1.1 Breast Cancer Screening Today

Screening is testing of asymptomatic (without symptoms) and symptomatic women. Mammograms identify abnormalities and determine their location in the breast. If a biopsy of the area in question is positive, treatment includes surgical removal of the cancer followed by radiation and medical therapy, if indicated. The standard protocol in the United States for Breast Cancer screening includes an annual clinical breast exam and mammogram for women over 40 years of age². Women with a family history of Breast Cancer or other indicators may be screened at an earlier age and more frequently. If the results are positive, further diagnostic testing may be prescribed and a biopsy may be taken. If the SBSII scan reveals a thermal pattern on analysis that meets established criteria and the mammogram is read as normal, FSM intends to contact the site PI. The study participant will then be encouraged to undergo additional standard diagnostic imaging tests. These additional tests are performed to assure that the patient has no evidence of abnormality utilizing advanced breast imaging techniques in use today. However, the additional tests ordered may indicate the need for further investigation prescribed by the study doctor. These imaging tests will be paid for by First Sense Medical.

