The core strengths of thermography are multi-faceted. Thermography is a fast, non-invasive, low cost and painless procedure performed without radiation exposure. Published studies support its use for early detection of breast tissue abnormalities and in identifying groups that may be at higher risk for developing breast cancer.

As an adjunct to mammography, thermography may be especially useful for screening younger, pre-menopausal women and women with dense breast tissue for whom mammography is less effective (Bleyer and Welch 2012).

³ Library, T.-S. R. (2011). "Thermology: Analytic Features." [A Professional's Guide To Breast Thermology](http://www.thermascan.com/professionals.html)
Retrieved January 4, 2013, from <http://www.thermascan.com/professionals.html>.

An automated platform for collecting thermal imaging data that provides objective, interpretative guidelines and standardized reporting would be an important adjunctive tool to aid in risk assessment and clinical decision-making in breast cancer screening.

Study Design and Selection and Exclusion of Subjects

1.4 Study Design: Testing a minimum of 2000 women receiving mammograms (comparing the SBSII/TS test results to the mammogram and biopsy results when applicable)

- a. SBSII test will be done before all mammograms, diagnostic or screening
- b. Women must wait a minimum of (3) days between mammography and the SBSII.
- c. If the SBSII test is positive and mammography is negative, FirstSense may request a breast ultrasound or MRI to determine the accuracy of SBSII. The acquisition order for MRI study will be done with prior approval by FSM.
- d. Any study subject, regardless of biopsy diagnosis and treatment, will continue to complete the SBS II imaging in conjunction with all future routine and necessary mammograms, not to exceed less than 6 months between each SBS II imaging, for up to 5 years from the start date of the subject's study participation. For subjects that undergo mastectomy after initial study participation, and are no longer completing routine and necessary mammograms, the SBS II will be completed with future routine and necessary breast MRI imaging, not to exceed less than 6 months between each SBS II imaging, for up to 5 years from the start date of the subject's study participation.

1.4.1 Subject Inclusion Criteria:

1. Female, over the age of 18 years of age.
2. Asymptomatic women or women who are being screened for breast abnormality.

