Thermal imaging data will be assessed by TS according to the internationally standardized thermology classification 'TH' scale, also known as the Marseilles system (Amalric, Brandone et al. 1978), which defines five categories of risk assessment.

The 3D, thermal and visible light data will be analyzed by TS to search for signs and criteria that indicate potential breast tissue abnormalities and arrive at a TH1-5 classification. Pattern recognition is used to identify blood vessels and measure the temperature points within these vessels. TS employs mathematical analysis to reduce the effective temperature variance and determine the probability of breast cancer. TS also uses mathematical techniques to measure magnitude of the focal areas on the breasts relative to the surrounding area. TS analyzes the average of approximately 10,000 data points and compares this analysis to the heat in any local hot spot. Sensitivity and specificity will be calculated by TS as described and data will be used to compare results with those from mammography and biopsy reports.

Clinically, a TH4-5 classification may result in a recommendation from the sponsor for further assessment. For study purposes, a comparison of the thermal categorization findings using the Marseille system to biopsy results will be analyzed. These results will provide a baseline for the semi-automated software analysis. Sensitivity and specificity will be calculated as follows:

TEST RESULT	CONDITION			Detection Rate
	Cancer	No Cancer	Total	
+ test	a (true positive)	b (false positive)	a+b	$\frac{a}{a+b}$ (positive predictive value=PPV)
- test	c (false negative)	d (true negative)	c+d	$\frac{d}{d+c}$ (negative predictive value=NPV)
Total	a+c	b+d	a+b+c+d	

\downarrow
 sensitivity = $\frac{a}{a+c}$

\downarrow
 specificity = $\frac{d}{b+d}$

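### Only a positive SBSII leads mammogram-negative women to study work-up, and later outcomes need not be collected, so the biopsy-based sensitivity in section 1.6 can read too high

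*Protocol*

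**What the plan says.** Section 1.6 (Specific Objective 2) sets the reference: "For study purposes, a comparison of the thermal categorization findings using the Marseille system to biopsy results will be analyzed". It then gives a 2×2 table with sensitivity a/(a+c), and counts its three phases in biopsy-proven cancers (up to 10, 45 and 45). Mammography is a further comparator: "data will be used to compare results with those from mammography and biopsy reports". Section 1.4 describes the design as "comparing the SBSII/TS test results to the mammogram and biopsy results when applicable".

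Work-up of mammogram-negative women is described in section 1.4 c: "If the SBSII test is positive and mammography is negative, FirstSense may request a breast ultrasound or MRI to determine the accuracy of SBSII". Section 1.1 says that if the thermal pattern meets criteria and "the mammogram is read as normal, FSM intends to contact the site PI", the woman is then encouraged to have further imaging. Section 1.3 has the same TH4/TH5 trigger, and section 1.6 adds: "Clinically, a TH4-5 classification may result in a recommendation from the sponsor for further assessment". The text shown gives no study work-up to a woman negative on both tests.

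On later outcomes, section 1.4 d says subjects "will continue to complete the SBS II imaging in conjunction with all future routine and necessary mammograms" for up to 5 years, and Intended Use of the Data lists follow-up breast imaging among the comparators. The Follow Up section says only that the sponsor *may* collect follow-up information, if the woman has additional breast testing.

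**The concern.** A cancer that mammography misses can enter the table in the first round (the index scan and its paired mammogram) through study work-up only if SBSII was positive. It then lands in cell a. A cancer that both tests miss belongs in cell c, but nothing in that round brings it to biopsy. The test under evaluation therefore helps to decide which cancers are counted.

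Two provisions could redress this: the repeat imaging in section 1.4 d and the follow-up imaging in Intended Use of the Data. Neither is tied to the section 1.6 table, and collection of outcomes is optional. An SAP can choose an estimator, but it cannot recover outcomes that were never collected.

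Section 1.3.1 presents higher sensitivity as the goal, and section 1.6 makes these results the baseline for the semi-automated software. An inflated baseline would misdirect that development.

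**Working it through.** The protocol derives no figure on this point, so there is none to reproduce. The check is a partial-verification calculation.

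**Inputs**
- M, mammogram sensitivity: 60–90% (section 1.3.1, item 2).
- S, true SBSII sensitivity: 95% (the published figure cited in the Introduction), and 70% as an assumption.
- v, share of SBSII-positive/mammogram-negative cancers found by triggered work-up: not given; shown at 1, 0.5 and 0.
- Assumed: the tests are independent given cancer, and every mammogram-positive cancer is biopsied.

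**Formula**
- TP = SM + S(1−M)v
- FN = (1−S)M
- Apparent sensitivity = TP/(TP+FN)

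**Example.** Take 100 cancers with S = 0.70 and M = 0.60. Both tests find 42, SBSII alone 28, mammography alone 18, and neither 12. With full work-up, TP = 42+28 = 70 and FN = 18, so the estimate is 70/88 = 79.5%. The 12 missed by both are not in the table.

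| True S | v = 1 (M = 0.90 to 0.60) | v = 0.5 (M = 0.90 to 0.60) | v = 0 |
|---|---|---|---|
| 95% | 95.5–96.9% | 95.3–96.2% | 95% |
| 70% (assumed) | 72.2–79.5% | 71.1–75.7% | 70% |

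**Sampling error.** With 45 cancers the Wald 95% half-width is 1.96√(0.95×0.05/45) = 6.4 points at 95% and 1.96√(0.70×0.30/45) = 13.4 points at 70%. The Wilson half-widths are 7.1 and 12.9.

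**Without independence.** Let D be the share of cancers missed by both tests. With S = 0.70 and M = 0.75, the shares are: both positive 0.45+D, SBSII only 0.25−D, mammogram only 0.30−D, with D from 0 to 0.25.
- None found by triggered work-up: (0.45+D)/0.75, from 60.0% (D = 0) to 93.3% (D = 0.25).
- Half found, D = 0: 0.575/0.875 = 65.7%, below the true 70%.
- All found, D = 0: 0.70/1.00 = 70.0%.

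Triggered work-up adds the same amount to numerator and denominator, so it can only raise the estimate. The net error can still go either way. At D = 0.25 no cancer is positive on SBSII alone, so the 93.3% owes nothing to triggered work-up and does not illustrate it.

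**Dilution.** Section 1.4.1, criterion 3 admits women with a biopsy already scheduled, who are verified whatever SBSII shows. If half of all cancers came this way (assumption), with v = 1 and M = 0.60:
- S = 0.70: 0.70/(0.70 + 0.15 + 0.09) = 74.5% instead of 79.5%.
- S = 0.95: 0.95/(0.95 + 0.025 + 0.015) = 96.0% instead of 96.9%.

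**With follow-up outcomes collected.** Let f be the share of mammogram-missed cancers found at the next routine mammogram. With v = 1 and S = 0.70, FN = (1−S)M + (1−S)(1−M)f.
- f = M: 70.2–73.5%.
- f = 0.5: 71.1–74.5%.

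Both compare with 72.2–79.5% when no later outcomes are collected.

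**The case against.** Five points can be put on the other side.

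- **The size is speculative.** The largest shift (9.5 points at 70%) needs an assumed sensitivity, the lowest mammogram value and every discordant cancer found. Work-up is only requested or encouraged, and MRI needs the sponsor's prior approval. Diagnostic mammograms and pre-scheduled biopsies dilute the effect further. This stands: the figures are upper illustrations.
- **Later cancers may be captured anyway.** Repeat imaging is planned for up to 5 years, and the Follow Up wording could be read as permission to gather extra records. The Study Schema figure and the case report form appendix are not shown, so a route given only there cannot be excluded. This tempers the point. Even so, no text shown links later findings to the section 1.6 table or requires their collection in women negative on both tests.
- **Some of the remedy is SAP content.** The exact window and the handling of unverified women may be left there. So may the way unbiopsied women enter specificity and PPV, which is not counted as an error here.
- **A follow-up window has its own error.** At true 70% and mammogram sensitivity 90%, the bias is 2.2 points. Two cancers arising after the scan and counted as false negatives would cost 3.0 points (31.5/47 = 67.0%). This stands, and is why both estimates should be shown.
- **This is feasibility work, not meant for marketing approval.** That limits the consequences. It does not remove them, because the estimate is the software's baseline.

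A reader might infer that sensitivity will necessarily be overstated. The documents do not support that: the uptake of work-up and the dependence between the tests are both unknown.

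**Conclusion.** The point holds in limited form. As written, first-round triggered work-up can add to cell a but not to cell c, and the data needed to correct this need not be collected. Sensitivity can therefore read too high.

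Under independence and full biopsy of mammogram-positive cancers, the upward bias is 0.5–1.9 points if the cited 95% is true. That is well inside the sampling error of a 45-cancer phase. It is 2.2–9.5 points at an assumed 70% with full work-up, 1.1–5.7 points with half, and zero with none. The zero holds under independence only. Unlike sampling error, this bias is not reflected in a confidence interval and does not shrink with more cases.

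It would go too far to conclude that the cited 95% is refuted, or that cancers missed by both tests can never come to light. The change is worth making because it is cheap and outcomes not collected cannot be recovered later.

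**What to change.** 1. **Follow Up section:** replace the permissive *may* with *will*, so that routine breast imaging and biopsy results are collected for all scanned women whatever the SBSII result.
2. **Section 1.6:** tie cancer status at each scan to those results by one rule that does not depend on SBSII, over a fixed period that includes the next routine mammogram. The exact length and the handling of unverified women may go to the SAP.
3. **Reporting:** state how many SBSII-positive/mammogram-negative women were worked up. Give sensitivity with and without cancers found only through that work-up, noting that the second figure is unbiased only if the tests are independent given cancer. Show first-round and follow-up-based estimates side by side.

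Separately, Intended Use of the Data says the results will not inform clinical decisions about subjects, while sections 1.1, 1.3, 1.4 c and 1.6 let them prompt further testing. These passages must be reconciled.

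**Cost:** protocol wording and collection of results that routine care already produces; no added procedure. The bias is reduced, not removed.
- Phase tables wait for follow-up.
- Some women stay unverified, mainly younger ones: entry is open to "Female, over the age of 18 years of age", but section 1.1 describes annual mammography only above 40.
- Repeat scans can still trigger work-up within the window.
- Each cancer arising after the scan counts as a false negative and lowers sensitivity by about 1.5 points at 70% with 45 cancers (31.5/46 = 68.5%).

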Protocol Title: Thermalogical Analysis of a cohort of women undergoing mammographic analysis.

Protocol Number: SBS-001

Version Number: 1

Version Date: 6/28/2017

Contact Information

Principal Investigator

[name]
University of Toledo
[name]
[contact]
E-mail:[contact]

Study Sponsor

[name] CEO
First Sense Medical, LLC
[name]
[contact]
Email: [contact]

Clinical Research Coordinator

[name]
Eleanor N. Dana Cancer Center
[name]
[name]
[contact]
Email: [contact]

Proprietary and Confidential

The information in this document is considered privileged and confidential, and may not be disclosed to others except to the extent necessary to obtain Institutional Review Board approval and informed consent, or as required by Federal and State laws. Persons to whom this information is disclosed should be informed that this information is privileged and confidential and that it should not be further disclosed.

Protocol Signature Page

Protocol No: SBS-001

Version Date: 6/28/2017

1. I agree to follow this protocol version as approved by Schulman and Associates IRB.
2. I will conduct the study in accordance with applicable IRB requirements, Federal regulations, and state and local laws to maintain the protection of the rights and welfare of study participants.
3. I certify that I, and the study staff, have received the requisite training to conduct this research protocol.
4. I have read and understand the information in the Investigators' Instructions for Use regarding the risks and potential benefits. I agree to conduct the protocol in accordance with Good Clinical Practices (ICH-GCP), the applicable ethical principles, the Statement of Investigator (Form FDA 1572), and with local regulatory requirements.
5. I agree to maintain adequate and accurate records in accordance with IRB policies, Federal, state and local laws and regulations.

[figure not shown]
University of Toledo Principal Investigator

Printed Name

Signature

Date

Study Schema

SBS II: positive for TH 4 and 5, negative for TH 0, 1, 2, 3, or 6

mammogram: negative for BIRADS 1 and 2, positive for BIRADS 0, 3, 4, 5, or 6

List of Abbreviations

CBE	Clinical Breast Exam
FSM	First Sense Medical®, LLC
SBSII	Sentinel Breast Scanner
TS	Therma-Scan Reference Laboratory, LLC (analyzes and produces report)
FS/TS	First Sense/Therma-Scan
MMG	Mammogram
PPV	Positive Predictive Value

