In addition, the data collected will be used to train, test and measure the accuracy of risk assessments utilized in manual thermography analysis when a cold air challenge is introduced into the clinical examination procedure. All data collected from study mammograms and biopsies will be divided into a phases consisting of all unblinded exams resulting in the identification of up to 10 biopsy proven cancer cases, a testing phase consisting of all double blinded exams resulting in the identification of up to 45 biopsy proven cancer cases, and a double blinded clinical trial consisting of all exams resulting in the identification of up to 45 biopsy proven cancer cases to measure the accuracy of manual thermography analysis as stated in Specific Objective 2.

1.7 Data analysis for Specific Objective 3:

The accuracy of the imaging system software to define the approximate location and identification of aberrant thermal signatures of increased metabolic activity will be compared to results found on analysis of mammographic and biopsy results.

IRB Ethics & Informed Consent:

The protocol, Informed Consent Form, and relevant supporting information must be submitted to the IRB for review and must be approved before the study is initiated. In addition, any subject recruitment materials must be approved by the IRB prior to use. This study will be conducted in accordance with the ethical principles that have their origin in the Declaration of Helsinki and that are consistent with the International Conference on Harmonization - Good Clinical Practice (ICH-GCP) guidance and applicable regulatory requirements. The study will be conducted in accordance with the regulations of the United States Food and Drug Administration (FDA) as described in 21 CFR Parts 50, 56 and relevant sections of 21 CFR Part 812, and the IRB requirements.

The sponsor must submit any change to the protocol to the IRB for review and approval before implementation. A protocol change intended to eliminate an apparent immediate hazard to subjects may be implemented immediately, provided the reviewing IRB is notified within 5 working days of implementation.

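### Section 1.6 admits exams of already-proven cancers to the accuracy tables, and the protocol's rules for scoring those exams conflict

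*Protocol*

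**What the plan says.** Section 1.6 splits the data into three phases, each made up of exams and each closed by a count of cancers. The first is "a phases consisting of all unblinded exams resulting in the identification of up to 10 biopsy proven cancer cases". A double-blinded testing phase of up to 45 cancers is listed next, and then "a double blinded clinical trial consisting of all exams resulting in the identification of up to 45 biopsy proven cancer cases". No phase is limited to one exam per woman or to exams before diagnosis.

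Section 1.4 item d makes repeat exams part of the design: "Any study subject, regardless of biopsy diagnosis and treatment, will continue to complete the SBS II imaging in conjunction with all future routine". This runs for up to 5 years and, after mastectomy, alongside breast MRI. The exclusion criteria in section 1.4.2 do not remove women with a known cancer.

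Three places bear on how such an exam is scored:

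- Section 1.2 gives five TH categories plus two others. One of these is TH-6, for a cancer already known from biopsy.
- The Study Schema holds the only stated positivity rules: "SBS II: positive for TH 4 and 5, negative for TH 0, 1, 2, 3, or 6" and "mammogram: negative for BIRADS 1 and 2, positive for BIRADS 0, 3, 4, 5, or 6".
- Section 1.6 says that the analysts look for "potential breast tissue abnormalities and arrive at a TH1-5 classification", which leaves no place for TH-6.

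The purpose in section 1.4 is "comparing the SBSII/TS test results to the mammogram and biopsy results when applicable", so both tests' results are to be set against each other and against biopsy.

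**The concern.** Sensitivity in the accuracy phase should describe how often the test flags a cancer that is not yet known. An exam of a cancer already proven by biopsy says nothing about that, yet the text lets it into the table. The schema then scores it in opposite directions for the two tests being compared. If TH-6 is never assigned, the exam still enters with a TH1-5 result, and nothing says whether a woman already diagnosed or treated belongs in the Cancer or the No Cancer column.

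The results are for device development and are not meant for a marketing submission. What is at stake is narrower: section 1.6 uses them as the baseline for the semi-automated software, and a baseline moved by coding could carry a reading method forward, or hold one back, for the wrong reason.

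**Working it through.** **The plan's own figures.** The protocol gives 10, 45 and 45 cancers (100 in all) and a minimum of 2000 women, without a derivation. There is no precision calculation to reproduce. The check therefore applies the protocol's own formula, sensitivity = a/(a+c), to an illustration.

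**Inputs**
- Cancers newly identified in the accuracy phase: 45 (section 1.6, upper limit).
- SBS II detections among them: 43, because 0.95 × 45 = 42.75; the 95% is the figure cited in the Introduction.
- Mammography detections among them, x: 27, 36 or 40 (60.0%, 80.0%, 88.9%), within the 60-90% in section 1.3.1.
- Known-cancer exams entering the Cancer column, m: 3 or 10. These counts are assumed; the protocol gives none.
- The mammogram of a known cancer is assumed to be coded BIRADS 6, which the protocol does not define.

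**SBS II sensitivity**
- Schema rule (TH-6 negative): 43/(45 + m).
- Same exams read TH4-5 (positive): (43 + m)/(45 + m).

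| m | TH-6 scored negative | Read TH4-5 |
|---|---|---|
| 0 | 43/45 = 95.6% | 43/45 = 95.6% |
| 3 | 43/48 = 89.6% | 46/48 = 95.8% |
| 10 | 43/55 = 78.2% | 53/55 = 96.4% |

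**Comparison with mammography.** With BIRADS 6 positive, mammography becomes (x + m)/(45 + m). The difference, SBS II minus mammography, is then:
- Schema rule: (43 − x − m)/(45 + m).
- Read TH4-5: (43 − x)/(45 + m).

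| x | m = 0 | m = 10, schema rule | m = 10, read TH4-5 |
|---|---|---|---|
| 27 | 16/45 = +35.6 | 6/55 = +10.9 | 16/55 = +29.1 |
| 36 | 7/45 = +15.6 | −3/55 = −5.5 | 7/55 = +12.7 |
| 40 | 3/45 = +6.7 | −7/55 = −12.7 | 3/55 = +5.5 |

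(Differences in percentage points.) Under the schema rule the sign reverses once m exceeds 43 − x, that is, more than 16, 7 or 3 exams. Under the TH4-5 reading the difference shrinks but cannot change sign.

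**Specificity.** If 10 such exams were instead counted as true negatives, an assumed 91.0% would hardly move. With 855 non-cancer exams (45 cancers at an assumed 5% yield) it becomes (0.91 × 855 + 10)/865 = 91.1%. With 4455 (1% yield) it becomes (0.91 × 4455 + 10)/4465 = 91.02%.

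**The case against.** The strongest reply is that TH-6 should not occur in the accuracy phase. Assigning it requires knowing the biopsy result. That phase is double blinded, the read described in section 1.6 ends at TH1-5, and the Data Management section denies the analysts access to the subject's ID. On that reading the falls to 89.6% and 78.2% do not arise, and the TH4-5 column is nearer the truth. This largely stands, and it is why the lower figures are only a worst case. It does not settle which column such an exam belongs in, or why the schema gives a result to a category that the read cannot produce.

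Second, section 1.6 speaks of exams that lead to cancers being identified, which suggests new cases. That may well be the intent, but the phrase governs the closing count; all exams still go into the phase.

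Third, the schema may serve another purpose. Section 1.4 item c allows extra imaging when SBS II is positive and mammography negative, and scoring TH-6 negative would keep known cancers from triggering it. That is possible, since section 1.6 does not cite the schema. But no other positivity rule is stated, so an analyst would probably use this one.

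A reader might go further and infer that accuracy is inflated because women whose exams trained the readers return in the accuracy phase. Section 1.6 does say "the data collected will be used to train, test and measure the accuracy of risk assessments", but it does not state the order of the phases, and nothing in the protocol lets the effect be sized. Nor is the lack of clustering methods or a software lock a fault here: those commonly sit in a statistical analysis plan, which is not at hand.

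**Conclusion.** The point holds in a limited form. The protocol's text admits exams of already-proven cancers to the accuracy tables, and its scoring passages for those exams do not agree. In the worst case, with 10 such exams all scored by the schema and all counted as cancer, an assumed 95.6% would drop to 78.2%. The comparison with mammography would reverse if mammography found 36 or 40 of the 45. If the same exams are read TH4-5, sensitivity moves by less than one point and no comparison reverses.

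It would be tempting to conclude that the study will understate SBS II or reverse the comparison. The documents do not support that. The number of such exams is unknown, blinding works against TH-6, many returning women will have been treated so that their column is undefined, and women followed with MRI after mastectomy may have no paired mammogram. What is established is an ambiguity that can matter and is easy to remove.

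**What to change.** In section 1.6, state three rules for the accuracy tables:

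1. An exam of a cancer already proven by biopsy before that exam is left out for both tests, or tabulated separately.
2. Each cancer is counted once, at the exam that led to its identification.
3. A new cancer later found in a returning woman still counts. Removing all her later exams would discard real detections.

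Reconcile the schema's scoring of TH-6 with the TH1-5 read in section 1.6. As a secondary step, report accuracy in women with no exam in an earlier phase as a sensitivity analysis; that subset may be small.

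The cost is wording and data handling, with no change to imaging or enrolment. The tables hold fewer exams, so intervals are slightly wider: the exact 95% interval is 84.9-99.5% for 43/45, against 87.5-99.6% for 53/55 when 10 known cancers are included and read positive. The extra precision given up comes from exams that carry no information on detecting new cancers.
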